### Technical Factors (Equipment, Energies)

Intensity modulated radiotherapy (IMRT) via any method (e.g., VMAT, static field IMRT) or Stereotactic Radiotherapy (SRT) is required. Any FDA cleared external beam radiation delivery system may be used (including conventional linear accelerators, cyberknife systems, tomotherapy, proton therapy, etc.). Treatment at NYULMC will be on Varian LINAC (TrueBeam or Edge) or Elekta Gamma Knife Perfexion Unit.

Image-guided radiotherapy with cone-beam CT along with daily treatment kV/kV imaging will be performed daily.

Imaging for treatment planning will be obtained with the patient in the same position and immobilization device as for treatment. All patients will be positioned via a combination of rigid immobilization and daily image guidance to ensure positioning accuracy of 3 mm or better, and of a magnitude that justifies the PTV margin applied.

### Localization, Simulation, and Immobilization

MRI fusion with CT are required for treatment planning. At least 1 of these scans must be of the patient immobilized in treatment position, and with image resolution of no worse than 1.5 mm x 1.5 mm x 3 mm. MRI sequences should include axial T1 post-contrast stereotactic image (such as MP-RAGE or FSPGR BRAVO). Contrast may be omitted if medically indicated. Additionally, a T2 sequence (e.g., FLAIR or T2, preferably stereotactic, thin slice, contiguous) is helpful to identify any non-enhancing tumor.

Immobilization must be rigid (e.g., thermoplastic masks). For daily treatment, localization will include the steps of a) immobilization with the same device used for simulation, and b) daily image guidance using at a minimum orthogonal pairs of radiographs aligned to DRRs as a computer-assisted process. Daily cone-beam CT will be used as well.

### Treatment Planning/Target Volumes

A GTV will be defined using the CT and MRI images.

The GTV includes the post-operative resection cavity if no residual enhancing or non-enhancing tumor is noted. The GTV also includes any non-enhancing tumor as identified on T2/FLAIR. T2/FLAIR signal consistent with edema is not included in the GTV. Therefore a distinction is made between T2 edema (typically without mass effect, sparing the cortical ribbon, obeying the grey/white junction, etc.) with T2 tumor (mass effect with sulcal effacement, involvement of the grey/white junction, obliteration of the cortical ribbon). Care is made to not include any enhancement or T2 signal on the post-operative scan that is due to post-surgical infarct. Fusion of the pre-operative MRI to determine initial extent of the tumor is helpful.

A PTV expansion that is justified based on image guidance and immobilization will be applied. Regardless of immobilization and localization methods, the PTV expansion should be no larger than 3 mm. Therefore, for stereotactic treatment, the PTV is typically 1 mm. For non-stereotactic treatment with IGRT, then the PTV is typically 3 mm.

### Critical Structures

Normal tissues to be contoured will include the brain, brainstem, optic nerves and chiasm. Planning risk volume (PRV) expansions the same size as the PTV expansion (e.g. If the PTV is 3 mm, then the PRV is 3 mm. For stereotactic machines, a PTV of 0 mm is acceptable; therefore the PTV = CTV = GTV + 5 mm in this instance) should be utilized for optic nerves and chiasm.

CONFIDENTIAL

This material is the property of the NYU School of Medicine and Langone Medical Center. Do not disclose or use except as authorized in writing by the study sponsor

Special consideration should be given to avoid doses greater than the prescription dose within the scalp as well as limiting the exit dose through the oral cavity and mucosa.

The treatment parameters should be modified to optimize the conformity of the prescription isodose volume to the target volume while minimizing dose to critical structures. OAR limits for newly diagnosed GBM are given in **Table A2**.

**Table A2: Normal Dose Limits (5 Fractions)**

Dose Metric	Per Protocol	Variation Acceptable	Deviation Unacceptable
Scenario (1): Previous radiation to the local area including critical organs at risk			
Maximum Dose (0.03 cc) to PRV for Optic Nerves, Chiasm	Less than or equal to 20 Gy photons - 20 Gy(RBE) protons	Greater than 20 Gy but less than or equal to 25 Gy photons – 25 Gy(RBE) protons	Greater than 25 Gy photons - 25 Gy(RBE) protons
Maximum Dose (0.03 cc) to Brainstem	Less than or equal to 24 Gy photons - 24 Gy(RBE) protons	Greater than 24 Gy but less than or equal to 25 Gy photons – 25 Gy(RBE) protons	Greater than 25 Gy photons - 25 Gy(RBE) protons
Scenario (2): No previous radiation to the local area or critical organs at risk			
Maximum Dose (0.03 cc) to PRV for Optic Nerves, Chiasm	Less than or equal to 25 Gy (the prescription dose) photons - 25 Gy(RBE) protons	Greater than 25 Gy but less than or equal to 26.25 Gy (105 % of the prescription dose) photons – 26.25 Gy(RBE) protons	Greater than 26.25 Gy (105% of the prescription dose) photons – 26.25 Gy(RBE) protons
Maximum Dose (0.03 cc) to Brainstem	Less than or equal to 25 Gy (the prescription dose) photons - 25 Gy(RBE) protons	Greater than 25 Gy but less than or equal to 26.25 Gy (105 % of the prescription dose) photons – 26.25 Gy(RBE) protons	Greater than 26.25 Gy (105% of the prescription dose) photons – 26.25 Gy(RBE) protons

Coverage of the PTV will be decreased in order to fulfill these limits.

The optic structures (chiasm and optic nerves) are kept to <350 cGy per fraction and the brainstem is allowed a D05 (the dose encompassing 5% of volume) of 600 cGy per fraction so that no more than 5% of the brainstem receives 600 cGy per fraction.

Radiotherapy dose constraints are based on the radiation therapy dose specifications in RTOG 1205.

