**Dose Specifications**

Photons: Treatment shall consist of 25 Gy delivered in 5 fractions delivered over 5 consecutive treatment days. The treatments may extend over the weekend (e.g., 5 treatment days over 8 calendar days.) Target coverage and homogeneity limits and deviations are listed in **Table A1**.

Protons - Absorbed dose: Doses are expressed in units of RBE-weighted absorbed dose,  $D_{RBE}$ . For protons the RBE is taken to be 1.1.  $D_{RBE} = 1.1 \times D$ , where D represents the absorbed dose in Gy. Treatment shall consist of 25 Gy(RBE) delivered in 5 fractions. Target coverage and homogeneity limits and deviations are listed in the **Table A1** below.

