**Table A1: Target Coverage and Dose Limits**

Dose Metric	Per Protocol	Variation Acceptable	Deviation Unacceptable
Volume of PTV covered by the prescription dose of 25 Gy photons - protons 25 Gy(RBE)	Greater than or equal to 95% of the PTV should receive greater than or equal to 25 Gy photons - protons 25 Gy(RBE)	Greater than or equal to 90% of the PTV receiving greater than or equal to 25 Gy photons - protons 25 Gy(RBE)	Less than 90% of the PTV receiving greater than or equal to 25 Gy photons - protons 25 Gy(RBE). Coverage less than 90% is acceptable in areas of OAR/PTV overlap.
Minimum dose to the PTV (0.03 cc)	Greater than or equal to 21.25 Gy (85% of the prescription dose) photons – protons 21.25 Gy(RBE)	Greater than or equal to 20 Gy (80% of the prescription dose) photons – protons 20 Gy(RBE); Minimum doses of less than 20 Gy are acceptable if they occur due to OAR/PTV overlap	Less than 20 Gy (80% of the prescription dose) photons – protons 20 Gy(RBE); Minimum doses of less than 20 Gy are unacceptable unless they occur in regions of OAR/PTV overlap
Maximum dose to the PTV (0.03 cc)	Less than or equal to 30 Gy (120% Rx Dose)	Less than or equal to 32.5 Gy (130% Rx	Greater than 32.5 Gy (130% Rx Dose)

CONFIDENTIAL

This material is the property of the NYU School of Medicine and Langone Medical Center. Do not disclose or use except as authorized in writing by the study sponsor

	photons – protons 30 Gy(RBE). For SRT, this represents a plan prescribed to the 84% or greater Isodose line)	Dose) photons – protons 32.5 Gy(RBE). For SRT, this represents a plan prescribed to the 80% isodose line)	photons – protons 32.5 Gy(RBE) or an isodose line less than 80% for a radiosurgical plan)
--	--	---	---

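### Attachment 6 contradicts itself on two radiotherapy limits: the brainstem D05 allowance (30 Gy) exceeds what Table A2 grades unacceptable, and Table A1 equates 130% of dose with the 80% isodose line

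*Combined protocol and SAP*

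**What the plan says.** All of this is in Attachment 6 of the combined protocol and SAP.

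- **Prescription (Dose Specifications).** "Treatment shall consist of 25 Gy delivered in 5 fractions delivered over 5 consecutive treatment days". Table A2 is also headed as applying to five fractions.
- **Brainstem, Table A2.** The metric is the maximum dose to 0.03 cc. Where the local area was irradiated before (Scenario 1), the unacceptable grade is "Greater than 25 Gy photons - 25 Gy(RBE) protons". Where it was not (Scenario 2), it is "Greater than 26.25 Gy (105% of the prescription dose) photons", with the matching proton figure.
- **Between the table and the text.** "Coverage of the PTV will be decreased in order to fulfill these limits".
- **Brainstem, text below Table A2.** "the brainstem is allowed a D05 (the dose encompassing 5% of volume) of 600 cGy per fraction". The sentence goes on to restate this as a ceiling on the share of the organ that may reach that dose. It is not confined to one scenario or to another fractionation.
- **PTV maximum, Table A1.** Per protocol is up to 30 Gy (120%), described for stereotactic radiotherapy (SRT) as the 84% isodose line or higher. Acceptable variation is up to 32.5 Gy (130%), described as the 80% isodose line. A deviation is unacceptable above 32.5 Gy, or if a radiosurgical plan uses an isodose line below 80%.

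**The concern.** The brainstem has two limits, and the one worded as an allowance lies above the level that the other calls unacceptable. The two isodose descriptions in Table A1 cannot both follow from the same dose arithmetic, although the row uses Gy and isodose as if they were interchangeable.

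These are organ-dose and deviation-grading thresholds in a re-irradiation trial. Inclusion criterion 8 requires prior CNS radiotherapy, although that need not have reached the brainstem, which is why Table A2 has two scenarios. Several sites will plan treatment with different delivery systems. If the text and the tables disagree, two sites could plan or grade the same case differently and each cite Attachment 6.

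**Working it through.** **Inputs.** Prescription 25 Gy in 5 fractions, so 5 Gy per fraction (Dose Specifications). Brainstem D05 of 600 cGy per fraction (text below Table A2). Brainstem 0.03 cc maximum: unacceptable above 25 Gy or above 26.25 Gy (Table A2). PTV maximum of 30 and 32.5 Gy, with 84% and 80% isodose lines (Table A1).

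**Reproducing the plan's own percentages.** 0.80 × 25 = 20 Gy; 0.85 × 25 = 21.25 Gy; 1.05 × 25 = 26.25 Gy; 1.20 × 25 = 30 Gy; 1.30 × 25 = 32.5 Gy. All match the tables. Only the isodose conversion fails.

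**1. Brainstem**

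- Total D05 allowance: 6.0 Gy × 5 = 30 Gy; 30/25 = 120% of prescription.
- Table A2 thresholds per fraction: 25/5 = 5.0 Gy (500 cGy) and 26.25/5 = 5.25 Gy (525 cGy). Both are below 600 cGy.
- D05 and the 0.03 cc maximum are different metrics, so their ordering has to be established. The hottest 5% of the organ contains the hottest 0.03 cc whenever 0.05 × volume ≥ 0.03 cc, that is, volume ≥ 0.03/0.05 = 0.6 cc. Above that volume, the 0.03 cc maximum is at least D05.
- The documents give no brainstem volume. Over an assumed range of 1 to 40 cc, 5% is 0.05 to 2.0 cc, always more than 0.03 cc.
- A plan with D05 at 30 Gy therefore has a 0.03 cc maximum of at least 30 Gy, which is at least 30 − 25 = 5 Gy above the Scenario 1 threshold or 30 − 26.25 = 3.75 Gy above the Scenario 2 threshold.
- If both limits apply, avoiding an unacceptable grade holds D05 to at most 500 or 525 cGy per fraction. The top 600 − 500 = 100 cGy, or 600 − 525 = 75 cGy, of the written allowance can never be used.

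**2. Isodose line**

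This assumes that isodoses are normalised to the plan maximum, taken to lie in the PTV, so maximum = prescription ÷ isodose fraction.

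| Stated maximum | Stated isodose | Maximum implied by that isodose | Isodose implied by that maximum |
|---|---|---|---|
| 30 Gy (120%) | 84% or greater | 25/0.84 = 29.76 Gy (119.0%) | 25/30 = 83.3% |
| 32.5 Gy (130%) | 80% | 25/0.80 = 31.25 Gy (125%) | 25/32.5 = 76.9% |

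The first row agrees apart from rounding. The second does not, and rounding cannot turn 76.9% into 80%. Plans prescribed to the 77%, 78% and 79% lines have maxima of 32.47, 32.05 and 31.65 Gy. Each is within the 32.5 Gy limit for acceptable variation, yet each falls under the clause that makes an isodose below 80% unacceptable.

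**The case against.** **Brainstem.** A 0.03 cc maximum and a D05 are two dose-volume limits on one organ, and plans routinely have to meet several at once. The D05 sentence can be read as an upper bound, and it does not say that Table A2 may be exceeded. Only Table A2 assigns grades, and the instruction to reduce PTV coverage follows it directly. A planner who applies both limits will simply follow Table A2, and no plan is then graded differently. This much stands. It shows that the sentence is harmless on one reading, but on that reading the sentence has no effect, and its wording as an allowance invites the other reading. No sentence states precedence.

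A reader might infer that the conflict covers every plan with a 0.03 cc maximum above 25 or 26.25 Gy and a D05 at or below 30 Gy. The documents do not support that: meeting one limit and failing another is ordinary when several apply. The incompatibility lies in the part of the D05 allowance that Table A2 makes unusable.

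A reader might also infer that the trial authorises 30 Gy to part of the brainstem. The grading in Table A2 and the coverage instruction point the other way.

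**Isodose.** The mismatch touches only SRT plans from 76.9% to just under 80%, and it depends on a normalisation that the documents do not state. Since the unacceptable cell joins its two tests with an or, a 78% plan can be called unacceptable on that cell alone. That also stands, but the adjacent cell still accepts the same plan on its Gy limit, and the stated equivalence remains false under that normalisation.

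**Conclusion.** Wrong as written, on both points; minor severity.

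The brainstem conclusion rests on five fractions, which the protocol fixes, and on a brainstem larger than 0.6 cc. The isodose conclusion rests on normalisation to the plan maximum, and the affected band is maxima above 31.25 and up to 32.5 Gy.

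The practical effect is probably limited. Section 4.2 excludes primary brainstem and recurrent infratentorial tumours, Table A1 accepts lower coverage where the target overlaps an organ at risk, and only the tables carry grades. Neither point touches the sample size or the analysis. Nothing here shows that any patient would be over-dosed. What is shown is that the attachment does not give one consistent answer.

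**What to change.** In Attachment 6, the sponsor should:

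1. reconcile the D05 sentence with the brainstem rows of Table A2, and state which brainstem limit governs planning and which governs deviation grading;
2. make the Gy and isodose figures in the PTV maximum row of Table A1 agree arithmetically, and state the normalisation used.

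Which limit is right, and which passage should change, is for the sponsor to decide. The cost is an amendment to one attachment and a notice to sites.

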### Documentation Requirements

At the completion of treatment, the following should be forwarded to the overall Principal Investigator listed below. Investigators must submit the following information:

- Daily treatment record.
- Radiotherapy summary.
- Pre-study CT or MRI (the Scan used to delineate the target volumes for planning. Submit the entire series and specify which one was used for planning).
- Isodose distributions displayed on orthogonal planes or, if not possible, on multiple transverse slices through each target.

CONFIDENTIAL

This material is the property of the NYU School of Medicine and Langone Medical Center. Do not disclose or use except as authorized in writing by the study sponsor

Data should be submitted to:

[name], PhD  
Laura and Isaac Perlmutter Cancer Center  
NYU Langone Medical Center  
[name]  
[name]

CONFIDENTIAL

This material is the property of the NYU School of Medicine and Langone Medical Center. Do not disclose or use except as authorized in writing by the study sponsor

## 15.7 Attachment: 7

### **Research Biomarker/Correlative Studies: Background and Rationale**

**Note:** This study involves collection of required archival tumor tissue and blood specimens for research as well as collection of an optional tumor specimen if a biopsy is required during or after protocol therapy. All patients will be given the option to have leftover research specimens after study completion and completion of protocol-defined research studies banked for future research at the time of informed consent. See **Section 9.1.1** for details on leftover research samples.

#### **A. Research Specimens to be Collected**

##### **1. Archival tumor tissue**

A paraffin-embedded or frozen tumor-tissue block with a minimum of 1 cm^2 of tumor surface area containing at least 20% viable tumor from a tissue specimen that demonstrates one of the two criteria specified below (also in **Inclusion Criteria 4a**). If a tumor block cannot be submitted, then 20 unstained 5-micron slides from the tumor specimen must be submitted.

(A) Histopathological evidence of glioblastoma (WHO grade IV) on a progressive tumor specimen after treatment with temozolomide or PCV chemotherapy. The diagnosis of glioblastoma must be confirmed on central review by a study-designated neuropathologist at NYU at screening.

or

(B) Any progressive glioma with *IDH1* or *IDH2* mutation, regardless of WHO grade or histopathological diagnosis, may be eligible contingent on approval by the overall Principal Investigator if the progressive tumor specimen is found to have one of the genetic alterations below:

1. ≥20 somatic mutations per Mb by whole-exome DNA sequencing
2. Mutation in a mismatch repair (MMR) gene or other genes known to be associated with hypermutator phenotypes or microsatellite instability, including but not limited to *MSH2*, *MSH6*, *MLH1*, *POLE*, *PMS2*, *POLD* as determined by validated methods.
3. Microsatellite instability (MSI) as identified by polymerase chain reaction (PCR) or other validated methods.

##### **2. (Optional) Tumor Biopsy**

If subjects undergo tumor resections or biopsies during the study period after treatment initiation, or after progression on HFRT + Avelumab, a tumor specimen will be collected for research purposes. A section of frozen tumor or a FFPE block (surface area of 1 cm^2 containing at least 20% viable tumor, as described above in Section 6.8.2) from the tumor surgery is preferred. If a frozen tumor specimen or a tumor block cannot be provided, then 20 unstained 5-micron slides (preferably 10 slides from two different tumor blocks from the same surgery) from the tumor block should be sent.

Send all research tumor specimens (archival and optional tumor biopsy) to:

[name]

CONFIDENTIAL

This material is the property of the NYU School of Medicine and Langone Medical Center. Do not disclose or use except as authorized in writing by the study sponsor

Department of Pathology, NYU Langone Medical Center  
[name]  
[name]  
[name]  
[contact], [contact], [contact]  
Email: [contact]

### 3. Research Blood Samples

Research blood samples will be taken at only **2 timepoints**: Baseline (prior to Cycle 1, Day 1) and at Cycle 2, Day 1, as per the study procedures (**Section 6**) and the **Schedule of Events, Attachment 1**.

Refer to the study **Lab Manual** for specific processing, handling and shipping procedures for research blood specimens.

Research blood samples will be collected from all subjects as detailed below.

- **NYULMC subjects**: 40 mL (four 10 mL purple top EDTA tubes) of whole blood will be drawn and immediately sent to the below sites:
  - One (1) 10 mL tube will be sent to the Center for Biospecimen Research and Development (CBRD) at NYULMC for acquisition of whole blood, buffy coat, and plasma samples.
  - Three (3) 10 mL tubes will be sent to the Immune Monitoring Core (IMC) at NYULMC and immediately processed for isolation of PBMCs.
- **Subjects at other sites**: 30 mL of whole blood will be collected in two types of Streck tubes provided by NYULMC. All tubes will be shipped overnight to the CBRD at NYULMC per instructions in the **Lab Manual**. **\*Subsites should NOT schedule research blood draws on Fridays as the NYU CBRD will not be able to receive specimens on weekends.**
  - 10 mL will be drawn into one Streck Cell-Free DNA BCT® collection tube.
  - 30 mL total will be drawn into three 10 mL purple top EDTA tubes and immediately sent via overnight shipping to NYULMC. On arrival at NYULMC, the tubes will be sent immediately to the Immune Monitoring Core and immediately processed for isolation of PBMCs.

All blood samples from non-NYULMC sites should be sent to the CBRD at NYULMC at the address below, per instructions in the Lab Manual. Research blood specimens collected from NYULMC subjects will be transported immediately to either the CBRD or the IMC (address below) as described above. **\*Subsites should NOT schedule research blood draws on Fridays as the NYU CBRD will not be able to receive specimens on weekends.**

## B. Types of Planned Analyses

### I. Studies using Tumor Tissue Samples

- Whole-exome deep sequencing to assess hypermutation phenotype, estimation of the total mutation-associated neoantigens, and T cell receptor (TCR) diversity.
- RNA-Seq to assess expression of predicted mutation-associated neoantigens.
- Immunohistochemistry (IHC) to assess intratumoral PD-L1 expression
- IHC to determine tumor-infiltrating lymphocytes (TILs)

### II. Studies Using Blood Samples

- Flow cytometry for quantification of Treg and myeloid-derived suppressor cell (MDSC) levels
- Genomic DNA for paired tumor sequencing
- TCR deep sequencing to determine peripheral clonal T-cell expansion and TCR diversity
- Circulating tumor DNA analysis

## C. Specific Planned Analyses

### 1. Tumor Tissue Whole-Exome Deep Sequencing

**Objectives:** To assess the association between PFS6 and:

- A)** Presence of temozolomide-induced hypermutation phenotype;
- B)** Total predicted neoantigen load;
- C)** T cell receptor (TCR) diversity

**A) Hypermutation phenotype:** Patients with lower-grade *IDH* mutant gliomas (WHO grade II or III) that are treated with temozolomide or PCV chemotherapy and later proceed to have histopathologic transformation to GBM (WHO grade IV) nearly universally develop hypermutation phenotype within their tumors (see Background and Rationale, **Section 1.1**). Temozolomide and PCV chemotherapy therapy provide selection pressure for clones that have acquired mutations in mismatch repair (MMR) genes which then dominate subsequent recurrences and drive histopathological transformation to the highest grade (GBM, WHO grade IV). The hypermutation phenotype is a distinct signature consisting of mutations in MMR genes (80-90% of cases have *MSH6* mutation) and an extremely high mutation frequency (>30 mutations per Mb in hypermutant versus 1-2 mutations per Mb in non-hypermutant cases) with a striking preponderance of C:G>T:A transitions at CpC dinucleotides. Non-hypermutant progressive *IDH* tumors typically harbor 30-80 nonsynonymous mutations, whereas hypermutant *IDH* mutant GBMs typically harbor between 1,000 - 3,000 nonsynonymous mutations. Notably, these

CONFIDENTIAL

cases are not detectable using a standard five reference panel of microsatellite instability (MSI) markers recommended by the NCI.

We will compare the association of hypermutation phenotype between tumors that achieve PFS6 and those that do not. We will analyze archival transformed GBM tissue from all patients with whole-exome deep sequencing and define hypermutation as  $\geq 20$  somatic, nonsynonymous mutations per Mb with a concomitant preference for C:G>T:A transitions at CpC dinucleotides. If enough archival tumor material is available, we will examine the clonality of hypermutated tumors through whole-exome sequencing of multiple spatially distinct tumor samples. If feasible, we will assess whether achieving PFS6 is impacted by whether hypermutation occurs subclonally or constitutes the majority of the recurrent tumor.

**B) Total predicted neoantigen load:** We will compare the potential mutation-associated neoantigen load between tumors that achieve PFS6 and those that do not. Using somatic exome data, we will assess the hypermutant cases for their immunogenic potential in the context of each patient's major histocompatibility complex (MHC) haplotype. To assess the potential for mutant peptide binding, somatic exome data combined with each individual patient's class I HLA haplotype will be applied to an epitope prediction algorithm, which provides an estimate of the total number of mutation-associated neoantigens in each tumor.

**C) T cell receptor (TCR) diversity:** One strategy to reverse the suppression of tumor immune responses involves the use of radiation therapy (RT), which has been shown to augment anti-cancer immune responses and enhance the efficacy of immune therapies in systemic cancer preclinical models and patients. Preclinical studies examining combined radiotherapy and checkpoint inhibition indicate that each activate mostly non-redundant immune stimulating mechanisms and the major contribution of radiotherapy appears to be increasing T-cell receptor (TCR) diversity. RT induces major histocompatibility complex (MHC) class I presentation, increases antigen presentation, and increases cytotoxic T cell (CTL) recognition of irradiated cells and enhances the diversity of the TCR repertoire of the expanded peripheral T cell clones.

We will characterize the baseline pre-treatment intratumoral TCR diversity and use intratumoral TCR diversity data (e.g., the top 100 most frequent intratumoral TCR clonotypes) to examine TCR clonotype frequencies in pre-treatment (Baseline) and post-treatment (C2D1, 29 days post-initiation of Avelumab and 21 days after completion of HFRT) blood samples. Using combined tumor tissue and pre-treatment (baseline) blood, we will generate whole-exome sequencing data and analyze frequencies/counts of TCR clonotypes to estimate the TCR diversity. The Shannon's diversity index (DI) normalized to the number of reads ( $DI = -\sum(\text{piln } \pi_i) / \ln n$ , where  $n$  is the number of clones,  $\pi_i$  is the clonal frequency of the  $i$ th clone, and sigma is summed from  $i = 1$  to  $i = n$ ) was calculated for each sample. This gives a value between 0 and 1, where 0 is monoclonal and 1 is an even distribution of different clones.

**If Post-treatment tumor tissue is available:** Additionally, if patients undergo tumor resections or biopsies during study therapy or after progression on HFRT + Avelumab, we will whole-exome sequence multiple spatially distinct regions, if possible, of the progressive tumor to determine whether alterations in the clonal hypermutation distribution, TCR clonotype distribution or predicted neoantigens have occurred.

